5.2.3 Assessment of safety laboratory parameters

Safety laboratory samples will be analyzed at the investigator's local laboratory. Safety laboratory examinations will include haematology, biochemistry and urine examinations. All laboratory tests mentioned in Table 5.2.3: 1 should be performed at screening (Visit 1). All post screening laboratory testing is optional and should be performed at the discretion of the investigator and in accordance to the current standard of care. The recommended safety laboratory examinations laboratory tests can also be found in Table 5.2.3: 1.

Table 5.2.3: 1 Clinical laboratory tests

Category	Parameters	
Haematology	Haemoglobin, platelet count, and White Blood Cell (WBC)	
Chemistry	Electrolytes: Sodium, and potassium	
	Liver function tests: Alkaline phosphatase, aspartate amino transferase (AST/SGOT), alanine amino transferase (ALT/SGPT), γ-glutamyltransferase (GGT), total bilirubin	
	Renal function parameters: Blood urea/Blood Urea Nitrogen (BUN), creatinine	
	Other: Glucose, albumin, phosphorus, lactate dehydrogenase (LDH), total protein, and Creatine Phosphokinase (CPK); in case of pathological CPK further evaluation (e.g., by determination of isoenzymes, troponin assays, ECG exam) should be performed as clinically indicated.	
Urinalysis	pH, protein, glucose, blood/erythrocytes, leucocytes, nitrite; in case of pathological finding further evaluation should be performed and results documented	
Pregnancy test	β-HCG testing in urine or serum in Women Of Child-Bearing Potential (WOCBP) (see Section 4.2.3)	

5.2.4 Electrocardiogram

Twelve-lead ECGs will only be performed locally at the trial sites at the discretion of the investigator in accordance to local current standard of care for patients (see Flow chart). When performed, the investigator will review the ECG recording at the time of the visit and record any ECG abnormality that meets AE criteria.

5.2.5 Assessment of other safety parameters

5.2.5.1 Physical examination

A general physical examination (which includes measurement of height (in cm) and body weight (in kg)) will be performed at screening and at the time points specified in the Flow chart. The evaluation of the ECOG performance score will be performed only at Visit 1.

5.2.5.2 Vital signs

Vital signs (blood pressure and pulse rate after two minutes rest) and temperature (preferably oral and/or tympanic: if other locations are used the same location should be used at each time point when body temperature is measured) will be recorded at the time points specified in the Flow chart.

5.2.5.3 Left ventricular function

Left Ventricular Ejection Fraction (LVEF) as measured by Echocardiography (ECHO) or Multiple Gated Acquisition scan (MUGA) will be assessed if clinically indicated. The testing of this function and cardiac monitoring should be considered in patients that develop relevant cardiac signs/symptoms during treatment. In patients with an ejection fraction below the institution's lower limit of normal, cardiac consultation as well as afatinib treatment interruption or discontinuation should be considered.

5.3 OTHER

5.3.1 Other endpoint(s)

Not applicable.

5.3.2 Other assessment(s)

5.3.2.1 Documentation of diarrhoea

Patients will receive a diarrhoea diary for the first 2 cycles of Afatinib (Giotrif®) treatment. Patients will receive instructions on how to record daily diarrhoea events. A copy of the instructions and the diary will be provided in the ISF.

All data on diaries will be reviewed at visit 2 and 3 and will be checked against the reported AEs and adherence to the instructions in Section 10.1.1 (Management of diarrhoea and hydration status following treatment with afatinib).

Use of a daily recording diary will capture quantitatively diarrhea data (number of bowel movements and consistency of diarrhea).

The diary will be used as a tool for investigators in order to get more granular information on the severity and duration of diarrhoea and whether patients followed recommendations in terms of anti-diarrheal concomitant medication and sufficient hydration. The diary is also a tool for the patient which reminds to contact the investigator in case high number of bowel movements are present over some days or in case of any concerns.

Accurate and constant assessment of diarrhoea symptoms, timely initiation of anti-diarrheal medication at first signs of diarrhoea, appropriate anti-diarrheal medication dose modifications based on the daily diarrhea symptoms, and non-pharmacologic interventions will facilitate early and appropriate interventions to minimize the duration and severity of dose limiting afatinib-induced diarrhea.

Page 46 of 95

5.3.3 Pharmacogenomic evaluation

Not applicable.

5.4 APPROPRIATENESS OF MEASUREMENTS

CTCAE criteria are used in the assessment of adverse events in cancer patients. Although an updated version is published, in the present trial CTCAE version 3.0 will be used. As several pivotal oncology trials are currently ongoing with the investigational product that utilize CTCAE version 3.0, it is considered more appropriate to continue to collect safety data using the same criteria applicable.

5.5 DRUG CONCENTRATION MEASUREMENTS AND PHARMACOKINETICS

Not applicable since no pharmacokinetic data will be collected or analyzed in this trial.

5.6 BIOMARKER

5.6.1 Endpoints based on biomarker(s)

EGFR – Mutation analysis

As per Section 1.1, there is a strong rationale to identify predictive markers which are features at baseline that may predict responsiveness to ErbB TKI in this population.

Enrolment

The presence of an EGFR mutation is mandatory for trial enrolment. Hence, the EGFR mutation analysis must be performed prior to enrolment into the trial (i.e., before a patient is consented). Any EGFR mutation-positive result must be documented and the analysis can be performed using the institution's local testing methodology.

5.6.2 Methods of sample collection

Not applicable since no samples are being collected within the trial.

5.7 PHARMACODYNAMICS

Not applicable since no pharmacodynamic data will be collected or analyzed in this trial.

5.7.1 Pharmacodynamic endpoints

Not applicable since no pharmacokinetic or pharmacodynamic data will be collected or analyzed in this trial.

Proprietary confidential information.

Boehringer Ingelheim 08 Feb 2021 BI Trial No.: 1200.55

Doc. No.: U13-1326-02 Trial Protocol Page 47 of 95

5.8 PHARMACOKINETIC - PHARMACODYNAMIC RELATIONSHIP

Not applicable since no pharmacokinetic or pharmacodynamic data will be collected or analyzed in this trial.

6. INVESTIGATIONAL PLAN

6.1 VISIT SCHEDULE

6.1.1 Screening and dispensing visit

Patients considered for this trial will undergo an eligibility evaluation (see Flow Chart). If patients meet all eligibility requirements they will be dispensed drug for the first 28 day treatment cycle.

A contact is required 15 (\pm 3) days after the patient's first dose to assess any AEs.

6.1.2 Treatment and safety evaluation visits

Safety evaluation visits are to be conducted after afatinib (**Giotrif®**) administration, at Day 28 (-7/+2)/Visit 2, and every 28 (-7/+2) days onwards. Please refer to the required and optional procedures to be performed at these visits in the Flow Chart and in Section 6.2.1.

In the event of force majeure or other disrupting circumstances (e.g. pandemic, war,) patients visits may be performed remotely to collect/report study data such as adverse events, concomitant therapies, clinical evaluation of tumour by symptoms and study medication compliance check. Where permitted by local law and regulations, trial medication may be shipped directly to the patients' home or two bottles of trial medication may be dispensed at the beginning of a treatment cycle, so that the next visit can be performed remotely.

The investigator is responsible for determining the necessity and frequency of any additional/unscheduled visits as well as the extent of the evaluation (e.g., physical examination, laboratory testing, adverse events, etc.) performed at these visits. At a minimum the investigator should note in the patient's chart when an additional/unscheduled visit occurs and make relevant entries on the AE and medication dispensing eCRFs.

A treatment cycle is defined as 28 days.

6.1.3 End of Treatment (EOT) visit

All patients should be evaluated at the end of their trial treatment. This visit should be completed on the day of the patient's last dose on trial medication or up to 14 days later.

In the event of force majeure or other disrupting circumstances (e.g. pandemic, war,) patient visit may be performed remotely to collect/report study data such as adverse events, concomitant therapies, clinical evaluation of tumour by symptoms and study medication compliance check.

6.1.4 Follow-Up (FU) visit

Patients should be contacted 28 (-7) days after the EOT visit to follow-up on their general condition and any adverse events which were not yet recovered at the EOT visit or any AEs

that started since then. In addition, information regarding patients' status will be collected at this visit. This information can be obtained by a phone call.

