6.2.3 End of trial and follow-up period

The End of Treatment (EOT) visit marks the end of the patient's treatment in the trial, and should be conducted as soon as the patient discontinues trial medication (afatinib), and may occur at any time during the trial. The investigator may discontinue patients due to any of the reasons presented in Section 3.3.4.1.

Doc. No.: U13-1326-02 Trial Protocol Page 55 of 95

Table 6.2.3: 1 End of Treatment (EOT) Visit

	The following must be performed and information recorded in the patient's chart	What to include in eCRF
Physical examination	Physical examination results (see Flow Chart). The evaluation of the ECOG performance score will be performed.	Verify that this physical examination was performed and record results (see Flow Chart).
Disease Assessment	Disease Assessment will be based on the assessment of cancer related symptoms and, if available, radiologic assessments as per standard of care at the site.	Disease Assessment to be included on CRF.
ECG	An ECG may be performed at the discretion of the investigator.	Verify if an ECG was performed.
LVEF (Left Ventricular Ejection Fraction)	Cardiac left ventricular function assessment by either ECHO or (MUGA) only for patients with cardiac risk factors and those with condition that can affect LVEF, at the discretion of the investigator and in accordance to the current standard of care.	Verify if an ECHO (or MUGA) was performed.
Safety Laboratory Testing – Optional	Hematology, and Biochemistry examination. See Section 5.2.3 for recommended safety laboratory evaluations. Laboratory testing is optional at this visit and may be performed at the discretion of investigator and in accordance to the current standard of care. Refer to Section 5.2.3 for a list of recommended safety laboratory tests. If performed as part of a safety evaluation visit, the test results must be filed or recorded in the patient's chart.	Verify if all recommended safety laboratory testing was performed and that values were acceptable according to the protocol. If not, see Section 5.2.2.1 No lab values are to be recorded on the CRF.
Urine Examination –	Urine examination. (see Section 5.2.3 for recommended urine examinations).	Verify if all recommended safety Urine testing was performed.

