6.2.4 Follow-Up

The Follow-up (FU) visit should occur 28 (-7) days after the EOT visit.

Follow-up visits should be scheduled for patients who met the trial withdrawal criteria (see Section 3.3.4). This visit marks the end of the patient's participation in the trial. Patients will not be required to attend the clinic for this visit. The clinic staff will contact the patients or their caregivers by telephone and inquire about any adverse events that might have occurred since the last visit and if applicable follow up on any unforeseen pregnancy during the trial. All concomitant medication should be added to the patient's chart. The Patient Status eCRF will be completed at this time.

Any additional (unscheduled) follow-up visits should be scheduled for patients with unresolved SAEs, AEs, or laboratory abnormalities who have discontinued trial participation. These events must be followed until resolution or until agreement is reached between the local medical monitor and the investigator that further follow-up is no longer required.

Doc. No.: U13-1326-02 Trial Protocol Page 57 of 95

Table 6.2.4: 1 Follow-up (FU) Visit/EOT + 28 Days (-7)

	What to Include in the Patient's Chart	What to include in eCRF
Adverse events	Patients should be asked to report any hospitalizations, emergency treatments, or new medications as well as any general health issues that may have surfaced since their last visit. All the information collected should be recorded in the patient's chart. Refer to Sections: 5.2.2 and 5.2.2.2 for protocol specific requirements regarding the collection and reporting of adverse event information.	All relevant AEs and all SAEs.
Concomitant Medications	Patients should be asked to report any concomitant drug use (including, but not limited to,: non-prescription medications, anaesthetic agents, homeopathic/herbal remedies and dietary supplement preparations).	No concomitant medications will be recorded on eCRFs.
Patient Status	Document any information regarding the patient's status during the planned observation time (i.e., 28 days after the patient's last dose of medication).	Any new anti-cancer medication that the patient has taken since EOT visit.
	When applicable, every effort should be taken to collect and document information on date of death.	Date when the patient completed the planned observation time.
	Note: any AE which results in death is considered an SAE.	Date of death Patient's status

Page 58 of 95

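### The documents disagree on follow-up timing, and under the 28 (-7) rule the last scheduled adverse-event enquiry can fall up to 7 days before the 28-day window closes

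*Protocol*

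**What the plan says.** **Timing of the visits.** Protocol 6.1.3 says of EOT: "This visit should be completed on the day of the patient's last dose on trial medication or up to 14 days later". Protocol 6.1.4 says of FU: "Patients should be contacted 28 (-7) days after the EOT visit to follow-up on their general condition". The Flow Chart grid, Protocol 6.2.4 and Table 6.2.4: 1 repeat the 28 (-7) rule, and SAP 6.7 writes it out as 21 to 28 days after EOT.

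Two places differ. Flow Chart footnote # puts FU 28 days after EOT, and Protocol 3.3.4.1 asks for a follow-up visit 28 days later. Neither has a minus window.

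**Timing of safety collection.** These periods are counted from last dose and run through day 28:
- AE collection (Flow Chart footnote, Table 5.2.2.2:1)
- the residual effect period (Protocol 5.2.2.2, SAP 6.1)
- treatment-emergence (Protocol 7.3.3, which includes day 28; SAP 7.8.1)
- the planned observation time in Table 6.2.4: 1

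**Status of the FU contact.** Protocol 6.2.4 states: "This visit marks the end of the patient's participation in the trial". It adds: "The Patient Status eCRF will be completed at this time". Table 6.2.4: 1 asks for the patient's status "during the planned observation time (i.e., 28 days after the patient's last dose of medication" and, in the eCRF column, for this item: "Date when the patient completed the planned observation time".

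**The concern.** The safety windows start at last dose, whereas the final contact is timed from a visit that can itself take place on the day of last dose. A site that keeps to the 28 (-7) rule can therefore ask its last scheduled AE question before the window has closed. The Patient Status eCRF completed at that contact cannot truthfully record the end of a 28-day observation time that is still running.

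Safety is the primary endpoint (Protocol 5.1, SAP 5.1). At stake are AEs, serious AEs and deaths that begin between an early FU contact and day 28. The count of patients with any AE would hardly change. The tables of serious AEs and of AEs leading to death, planned in SAP 7.8.1, are where a missed late event would show.

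**Working it through.** **Inputs.** Take last dose as day 0.
- EOT day e = 0 to 14 (Protocol 6.1.3).
- FU offset f = 21 to 28 days after EOT (Protocol 6.1.4 and 6.2.4, SAP 6.7). The protocol's 28 (-7) gives 28 - 7 = 21 to 28, which reproduces the SAP's stated window.
- The safety window closes at the end of day 28.

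**Formulae.** FU day after last dose = e + f. Uncovered days = 28 - (e + f) when this is positive.

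**Range.** Earliest FU is 0 + 21 = day 21, and latest is 14 + 28 = day 42. FU can precede day 28 only if e + 21 < 28, that is, e is 6 or less.

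| EOT day | FU window (days after last dose) | Permitted FU days (of 8) before day 28 | Largest gap (days) |
|---|---|---|---|
| 0 | 21-28 | 7 | 7 |
| 1 | 22-29 | 6 | 6 |
| 2 | 23-30 | 5 | 5 |
| 3 | 24-31 | 4 | 4 |
| 4 | 25-32 | 3 | 3 |
| 5 | 26-33 | 2 | 2 |
| 6 | 27-34 | 1 | 1 |
| 7-14 | 28-35 to 35-42 | 0 | 0 |

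**Counts.** There are 15 x 8 = 120 permitted whole-day pairs. Early pairs: 7 + 6 + 5 + 4 + 3 + 2 + 1 = 28. Another 8 fall on day 28 and 84 fall later (28 + 8 + 84 = 120). Uncovered days summed over the early pairs: 7x1 + 6x2 + 5x3 + 4x4 + 3x5 + 2x6 + 1x7 = 84, a mean of 84/28 = 3.0 and a maximum of 7.

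**Without the -7.** FU at exactly EOT + 28 falls on day 28 (0 + 28) to day 42 (14 + 28), and no pair precedes day 28. One edge remains: with EOT on day 0 the call is made on day 28 itself, before a window that includes day 28 has ended.

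**The case against.** **The plan already closes the gap in places.** Footnote # and Protocol 3.3.4.1, taken literally, never put FU before day 28. This stands, and it is why the point is an inconsistency to be reconciled. A reader might infer that the whole plan is built around an early last contact, but these two places do not support that. They also do not settle the matter, because four places in the protocol and one in the SAP allow the earlier date.

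**The site keeps a duty to cover day 28.** Table 5.2.2.2:1 requires all AEs, serious AEs and deaths to day 28 to be reported. The FU cell for adverse events in the Flow Chart carries footnote 7, which appears to be the note requiring collection over those 28 days. For events still open, Protocol 6.2.4 says: "These events must be followed until resolution or until agreement is reached between the local medical monitor and the investigator". All of this stands and limits the loss. However, the extra visits in 6.2.4 are for unresolved events or laboratory abnormalities, and nothing schedules an enquiry about new events after an early FU contact.

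**Prompt EOT may not be typical.** A reader might infer from Protocol 6.2.3, under which EOT "should be conducted as soon as the patient discontinues trial medication (afatinib", that an EOT in the first week is the intended case. The documents do not support this. That instruction is tied to discontinuation, whereas the safety window is counted from last intake. Under Protocol 4.1.4.1, discontinuation can follow a pause of up to 6 weeks, so EOT may come well after last intake. From day 7 onward there is no gap.

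**A late event would still be tabulated if reported.** A reader might infer from SAP 6.1, which lists but does not tabulate data recorded after the last per-protocol contact, that a day-25 event after a day-21 contact drops out of the tables. SAP 6.1 does not say how a last contact before day 28 is handled. But SAP 7.8.1 assigns treatment-emergence by when the event occurred, up to day 28. The supportable concern is whether the event is found at all.

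**Conclusion.** The point holds as an inconsistency between sections, with a small loss of ascertainment possible under the more permissive rule. The final AE enquiry can fall on day 21 to 27 after last dose when EOT is on day 0 to 6 and the minus window is used. At most 7 of the 28 days after last dose are then left without a scheduled enquiry. Only new-onset events are exposed.

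The 28 of 120 date pairs should not be read as a proportion of patients. It weights every permitted pair equally, and the documents give no distribution of visit timing, so the share affected cannot be computed. It is probably small. No hypothesis test is planned, so no test result can change. The conclusion assumes whole-day counting and sites that keep to the stated windows.

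**What to change.** Reconcile the Flow Chart grid and footnote #, Protocol 3.3.4.1, 6.1.4 and 6.2.4, Table 6.2.4: 1 and SAP 6.7. The common rule should be that the FU contact takes place only once 28 full days have passed since last drug intake: no earlier than day 28, preferably day 29, with any tolerance running later. Day 29 covers the whole of an inclusive day-28 window and lets the Patient Status eCRF record a completed observation time. As a minimum, delete the -7, as footnote # and 3.3.4.1 already imply. That removes all 28 early pairs and leaves only the day-28 edge for an EOT on day 0.

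The change adds no visit, and FU can remain a phone call. For patients with an early EOT the call moves later by about a week at most: from day 21 to day 28 is 7 days, and to day 29 is 8. Protocol and SAP wording must be amended, and the protocol amendment needs ethics and competent-authority approval (Protocol 8.1). Protocol Section 11 gives 481 as the actual number entered, so the benefit is confined to patients who have yet to stop treatment.

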6.2 DETAILS OF TRIAL PROCEDURES AT SELECTED VISITS

The trial procedures are summarized in the Flow Chart.

6.2.1 Screening and run-in period(s)

Visit 1/Day -1 – Screening and dispensing visit

Informed consent must be obtained prior to any trial related procedures taking place.

Tests for which results are not already available as part of the patient's standard of care, may be ordered after the patient signs informed consent.

Prior to determining eligibility the investigator should: 1) review all information obtained at this visit, 2) review the inclusion/exclusion criteria and 3) confirm that the patient has discontinued all prohibited therapy or medications (see Sections 4.2.2 and 4.2.2.1) and an adequate washout period has passed.

Table 6.2.1: 1 Visit 1 /Day -1 – Screening and dispensing visit

	The following must be performed and information recorded in the patient's chart	What to include in eCRF
Informed Consent	Written informed consent must be obtained prior to any trial related procedures taking place.	Date of informed consent
Demographics	Obtain the following demographic data: sex, birth date, race, smoking and alcohol history	Sex, birth date, race, ethnicity, and smoking history

Doc. No.: U13-1326-02

08 Feb 2021

Page 50 of 95

Trial Protocol

	The following must be performed and information recorded in the patient's chart	What to include in eCRF
Medical history	Oncological and relevant non-oncological	History of NSCLC:
	history including details of previous treatment for NSCLC (including pathology)	Oncological and relevant non-oncological history including details of any previous treatment for NSCLC
		• The date of first histological diagnosis, the primary tumour site, the number and location of metastatic sites (bone, brain, liver, pleural effusion, other)
		Tumour assessment/stage at the time of diagnosis according to the TNM-classification
		• Previous surgeries for NSCLC
		• Previously administered chemo-, immuno-, hormone therapy will be reported including start and end dates, the treatment regimen with the number of courses (chemo-immunotherapy), the best response obtained (complete response, partial response, stable disease, progressive disease, unknown), and progression date.
		Previous radiotherapy - the total radiation dose and radiation field will be recorded
Inclusion and Exclusion criteria	Assessment of eligibility according to inclusion and exclusion criteria should be performed.	Verify that the patient has met all the inclusion and exclusion criteria.
Physical examination	Physical examination results (see Flow Chart). The evaluation of the ECOG performance score will be performed.	Verify that this physical examination was performed and record results (see Flow Chart).

Page 51 of 95

Table 6.2.1: 1 (continued) Visit 1/Day -1 – Screening and dispensing visit (Page 2 of 3)

	The following must be performed and information recorded in the patient's chart	What to include in eCRF
ECG	12-lead resting ECG may be performed at the discretion of the investigator.	Verify if an ECG was performed. Any abnormal results are reported on baseline conditions form.
LVEF (Left Ventricular Ejection Fraction)	Cardiac left ventricular function assessment by either ECHO (or MUGA) only for patients with cardiac risk factors and those with condition that can affect LVEF, at the discretion of the investigator and in accordance to the current standard of care.	Verify if an ECHO (or MUGA) was performed.
Safety Laboratory Testing	Hematology, and Biochemistry examination. See Section 5.2.3 for recommended safety laboratory evaluations. Blood samples may be collected to perform the following: - Retest for missing laboratory test results required to establish eligibility - Safety laboratory testing as deemed necessary by the investigator	Verify that all recommended safety laboratory testing were performed and that values met eligibility criteria according to the protocol. No lab values are to be recorded on the CRF.
Urine Examination	Urine examination. (see Section 5.2.3)	Verify if all recommended urine testing was performed. No lab values are to be recorded on the CRF.
Pregnancy test	β-HCG testing in urine or serum will be performed in females of childbearing potential (see Section 5.2.3). A negative result is required for enrolment in the trial.	Verify that β-HCG testing in urine or serum was performed and that patient is not pregnant.

Doc. No.: U13-1326-02 Trial Protocol Page 52 of 95

Table 6.2.1: 1 (continued) Visit 1/Day -1 – Screening and dispensing visit (Page 3 of 3)

	The following must be performed and information recorded in the patient's chart	What to include in eCRF
Adverse events	Patients should be asked to report any hospitalizations, emergency treatments, or new medications as well as any general health issues that may have surfaced since signing the informed consent form. All the information collected should be recorded in the patient's chart. Refer to Sections: 5.2.2 and 5.2.2 for protocol specific requirements regarding the collection and reporting of adverse event information.	All relevant AEs and all SAEs.
Concomitant Medications	Patients should be asked to report any concomitant drug use (including, but not limited to,: non-prescription medications, anaesthetic agents, homeopathic/herbal remedies and dietary supplement preparations).	No concomitant medications will be recorded on eCRFs.
Dispense Trial Medication	Dispense 1 bottle of afatinib (Giotrif®) for the 28 day treatment cycle (see Section 4.1.4.)	Record: dose dispensed, amount of bottles dispensed, all medication numbers and date of first dose administration

